	sponges to enhance cooling of the renal parenchyma during the	
	anhepatic phase of the operation.	
CONTROL	Normothermia (36.5-37.5 °C) during liver transplantation	
TREATMENT AND	romotiona (50.5 57.5 °C) during irver dunsplanation	
METHOD OF	Normothermia will be maintained using an ECD as well as standard	
ADMINISTRATION	measures after the induction of general anesthesia and throughout the	
	liver transplant operation.	
	Subjects will be on study for up to one year.	
DURATION OF	Screening: less than 1 day	
SUBJECT PARTICIPATION	Treatment: less than 1 day (during liver transplantation)	
	Follow-up: 1 year	
AND DURATION OF	The total duration of the study is expected to be 36 months. 24	
STUDY	months for subject recruitment and 12 for final subject follow-up.	
CONCOMMITANT	Allowed: N/A	
MEDICATIONS	Allowed. N/A	
MEDICATIONS	Prohibited: N/A	
FEELCACY		
EFFICACY EVALUATIONS		
PRIMARY ENDPOINT	Incidence of acute kidney injury within 72 hours after liver	
TRIMARI ENDI OINT	transplantation	
SECONDARY	 Distribution of the stages of acute kidney injury within 72 hours 	
ENDPOINTS	after liver transplantation	
	 Duration of intensive care unit stay 	
	 Duration of hospital stay 	
	 One-year survival rate 	
	 Need for renal replacement therapy within 7-days, at 30-days, and 	
	at 1 year after transplant	
	 Persistent renal dysfunction at 90-days and 1-year after transplant 	
	 Change in serum NGAL levels from baseline to 2 hours after 	
	reperfusion of the portal vein	
	 Change in urine NGAL levels from baseline to 2 hours after 	
	reperfusion of the portal vein	
OTHER	Percentage of intraoperative time within target temperature range	
EVALUATIONS	i i oreentage of intraoperative time within target temperature range	
LIALUAIIUNS	 	

SAFETY EVALUATIONS	 Time to reach normothermia upon initiation of re-warming (mild hypothermia arm) Number of units of blood products transfused (packed red blood cells, fresh frozen plasma, platelets, and cryoprecipitate) Incidence of surgical site infections within 2 weeks of LTx Intraoperative vasopressor doses
PLANNED INTERIM ANALYSES	When 50% of patients have completed the study, an interim analysis for efficacy will be conducted by an independent data safety monitoring board (DSMB).

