 - Defined as significant bleeding that is not attributable to vascular injury in the presence of ongoing severe clinical coagulopathy despite aggressive treatment (fresh frozen plasma 15 mL/kg, cryoprecipitate 10 units x 2 doses, and the administration of antifibrinolytics). While coagulopathy is a clinical diagnosis during LTx, we would consider persistent INR > 4 or fibrinogen < 75 mg/dL after the aggressive treatment above as laboratory evidence of severe coagulopathy.
 - Severe upper gastrointestinal (GI) bleeding at the time of ECD insertion
 - It is common to have mild upper GI bleeding after insertion of a standard orogastric tube during liver transplant, so only blood return of > 500 mL will be considered an AE.
 - Severe hypothermia
 - \circ < 33 °C for greater than 30 minutes
 - Oropharyngeal, dental, or esophageal trauma
 - Perforation or damage to the ECD
 - Intraoperative cardiac arrhythmias requiring treatment ³¹ excluding bradycardia typically seen at the time of reperfusion of the liver graft.

- Intraoperative myocardial ischemia or infarction.
- Discomfort (oropharyngeal pain, dysphagia, odynophagia) patients will be asked about these symptoms post-operatively
- Surgical site infections (SSIs) prior to discharge from the hospital after LTx, or within two weeks of LTx (whichever comes first).³⁸

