9.1.6 Adverse Events

Information regarding occurrence of adverse events will be captured throughout the study. Duration (start and stop dates and times), severity/grade, outcome, treatment and relation to study drug will be recorded on the case report form (CRF).

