10 EVALUATIONS BY VISIT

10.1 Visit 1 (Day 1, before and during LTx)

- 1. Review the study with the subject (subject's legal representative) and obtain written informed consent and HIPAA authorization and assent, if appropriate.
- 2. Assign the subject a unique screening number.
- 3. Record demographics data.
- 4. Record medical history, including a history of acute kidney injury, ascites, or hepatic encephalopathy, including diagnosis date, and prior treatments (dialysis, continuous renal replacement therapy (CRRT), large volume paracentesis).
- 5. Record concomitant medications.

- 6. Perform a complete physical examination.
- 7. Perform and record vital signs.
- 8. Perform and record oximetry.
- 9. Perform and record results of blood pressure testing.
- 10. Randomize subject (see Section 8.1).
- 11. Place ECD after induction of general anesthesia.
- 12. Implement intraoperative temperature protocol according to randomization (see Section 8.3).
- 13. Collect blood for ABGs (see Section 9.2) and NGAL determination (Section 9.3.1).
- 14. Collect urine for NGAL determination (see Section 9.3.2).
- 15. Remove ECD at the end of surgery.
- 10.2 Visit 2 (Follow-up prior to hospital discharge, window of 2 ± 1 weeks after LTx)
- 1. Record any Adverse Experiences.
- 2. Record changes to concomitant medications.
- 3. Perform complete physical examination.
- 4. Perform and record vital signs.
- 5. Perform and record oximetry.
- 6. If surrogate consent was obtained for the subject, and subject has now regained capacity, re-consent the patient for use of study data.

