11.2.1 Serious Adverse Experience Reporting

Study sites will document all SAEs that occur (whether or not related to study treatment) per UCSF CHR Guidelines. The collection period for all SAEs will begin after informed consent is obtained and end after procedures for the final study visit have been completed.

In accordance with the standard operating procedures and policies of the local Institutional Review Board (IRB)/Independent Ethics Committee (IEC), the site investigator will report SAEs to the IRB/IEC.

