- The change in urine NGAL level from baseline to 2 hours after reperfusion of the portal vein will be summarized by median and interquartile range by arm and compared by two-sample t-tests, or Mann-Whitney U tests if the normality assumption does not hold.

Safety and tolerability data will be summarized by treatment group.

Adverse event rates will be coded by body system and MedDra classification term. Adverse events will be tabulated by treatment group and will include the number of patients for whom the event occurred, the rate of occurrence, and the severity and relationship to study treatment.

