APPENDIX 1. SCHEDULE OF STUDY VISITS

	VISIT 1 (Day 1, before and during liver transplant)	VISIT 2 (Day 2, prior to hospital discharge, approximately 2 weeks after LTx) ^A
Informed Consent	X	X ^B
Medical History	X	
Complete Physical Exam	X	X
Height	X	
Weight	X	
Vital Signs	X	X
Oximetry	X	X
Randomization	X	
Administration of Study Treatment	X	
Blood and Urine collection	X	
Initiate Subject Diary	X	
Subject Diary Review		X
Concomitant Medication Review	X	X
Adverse Experiences		X

^A ±1 week

^B Consent from subject will be obtained for use of study data if the patient lacked capacity and Surrogate Consent was obtained during Visit 1.

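### The synopsis counts surgical site infections to two weeks, but Section 5.3E stops at discharge if that is earlier, so under 5.3E the observation window depends on length of stay

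*Combined protocol and SAP*

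**What the plan says.** The Protocol Synopsis, under Safety Evaluations, lists "Incidence of surgical site infections within 2 weeks of LTx". It makes no reference to discharge. Section 5.3, item E, lists "Surgical site infections (SSIs) prior to discharge from the hospital after LTx, or within two weeks of LTx (whichever comes first"), so counting ends at the earlier of the two dates. Both are current text.

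Other text bears on when adverse events are collected, but none of it defines the SSI window:

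- Section 9.1.6: "Information regarding occurrence of adverse events will be captured throughout the study". The synopsis adds "Subjects will be on study for up to one year".
- Section 10.2 describes Visit 2 as "Follow-up prior to hospital discharge, window of 2 ± 1 weeks after LTx". Appendix 1 places it "prior to hospital discharge, approximately 2 weeks after LTx", with a tolerance of one week either way.
- Section 11.2.1 has serious adverse event collection "end after procedures for the final study visit have been completed".
- Section 4.1 plans remote follow-up through the electronic medical record (EMR) for one year, without saying that SSIs are taken from it.

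On analysis, Section 15.4 states "Safety and tolerability data will be summarized by treatment group" and tabulates adverse events by arm as patient counts, rates, severity and relationship to treatment. Duration of hospital stay is secondary endpoint C in Section 5.2.

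**The concern.** SSI is a harm that Section 2.1 itself links to hypothermia. The same section expresses confidence that rewarming and antibiotics will prevent it, and the SSI count is the data against which that confidence can be checked.

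With two definitions in force, two analysts could report different incidences from the same data and both be following the protocol. The 5.3E version has a further weakness: how long a patient is observed for SSI depends on when that patient goes home. Section 2.1 associates more severe kidney injury with longer stay, so an intervention that reduced kidney injury could also change stay. If stay differed by arm, the time in which an infection could be counted would differ too, and the tabulated proportions would not be like for like. The distortion could run in either direction.

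There is also a possible link to safety monitoring. In Section 15.5.2 the expected incidence below 5% refers to severe and life-threatening events on the 5.3E list. The sentence that sets the trigger above 10% does not name that list. Whether a severe SSI arising after discharge enters the monitored count therefore depends on how that sentence is read.

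**Working it through.** The plan gives no SSI rate or length of stay, so there is no figure of its own to reproduce. The check is a comparison of the two definitions, followed by arithmetic.

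**1. The definitions side by side.** Let L be the day of discharge.

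- Synopsis window = 14 days.
- Section 5.3E window = min(L, 14) days.

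They agree when L ≥ 14 and differ when L < 14. For example, a patient discharged on day 9 who develops an SSI on day 12 is counted under the synopsis and not under 5.3E.

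**2. Share of the window lost, per patient.** Unobserved share = (14 − L)/14 for L < 14, otherwise 0.

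- L = 7: 7/14 = 50%
- L = 10: 4/14 = 29%
- L = 12: 2/14 = 14%
- L ≥ 14: 0%

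This is a share of time. It equals the share of infections missed only if onset is spread evenly over the 14 days.

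**3. Arm-level illustrations.** Every input on stay, SSI risk and onset below is an assumption. True 14-day risk is the same in both arms, so the correct risk ratio is 1.00.

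*Whole-arm difference in stay.* Assume a constant hazard, λ = −ln(1 − R)/14, so counted risk = 1 − exp(−λ·min(L, 14)). Take everyone in one arm discharged on day 8 and everyone in the other on day 10.

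- R = 5%: 2.89% against 3.60%, ratio 1.25 (1.245)
- R = 10%: 5.84% against 7.25%, ratio 1.24
- R = 20%: 11.97% against 14.73%, ratio 1.23

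At R = 10% and 101 per arm, that is 101 × (0.0725 − 0.0584) = 1.4 counted events of difference. Stays of 8 against 12 days give ratios of 1.45 to 1.49.

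*Partial difference in stay.* Assume log-normal stays (log-SD 0.4, minimum 4 days), even onset, and stay independent of SSI. For medians of 10, 14 and 21 days, simulation with 2,000,000 draws gives 28%, 13% and 3% of 14-day SSIs uncounted. At 10% risk there are 101 × 0.10 = 10.1 true events per arm, so about 2.8, 1.3 and 0.3 go uncounted. A 7-day minimum gives 26%, 12% and 3%. Now shift stay by 5 days in 20.4% of one arm (0.68 × 0.30, the planned absolute reduction in kidney injury). With the 4-day minimum, the counted risk ratio is 0.93 to 0.98 for shorter stay and 1.005 to 1.06 for longer stay. The largest gap is about 0.5 event at 10% risk.

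*Later onset.* Keep that partial shift, with median stay 10 days and minimum 4, but place onset evenly over days 4 to 14. Then 39.3% are missed and the ratios are 0.878 and 1.105. The gap at 10% risk is 10.1 × 0.607 × (1 − 0.878) = 0.75 event.

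The ratios therefore run from about 0.88 to 1.49 depending on the scenario. None of these figures is a bound.

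**The case against.** The strongest reply is that the synopsis line is shorthand for the fuller wording in 5.3E, and that an in-hospital window is a legitimate choice because patients are then observed directly. SSI is descriptive, with no stated test of its own, and every arm-level number above is assumed. An infection that develops near discharge may also prolong the stay and so be counted, which would make the illustrated losses too high. All of this limits the importance of the point. It does not remove it: the synopsis line carries no discharge limit, and an in-hospital window still gives unequal observation time whenever stay is under 14 days.

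Some stronger readings are tempting but unsupported:

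- *A reader might infer that adverse events are collected only at Visit 2, because Appendix 1 marks them only there.* That row is also blank at Visit 1, although most of the 5.3E events are intraoperative. The schedule cannot be a complete statement of collection times, and Section 9.1.6 points the other way.
- *A reader might infer that the Visit 2 tolerance shows discharges from day 7.* It is a visit window centred on about two weeks. The plan allows for earlier discharge but does not say how often it happens.
- *A reader might infer that the stopping rule misses post-discharge SSIs.* That follows only if the trigger above 10% is limited to the 5.3E list, which its sentence does not say.
- *A reader might infer that the hypothermia arm's SSI count will be biased downward, or that any bias must be small.* Without stay by arm, neither direction nor size can be established.

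The detailed analysis plan promised in Section 15 could choose a window. However, it is required only before the final analysis, by which time SSIs have been collected and the monitoring board has met.

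**Conclusion.** The point holds as a conflict between two current definitions, and the 5.3E definition makes SSI observation time depend on a post-randomisation endpoint. That much follows from the text and needs no assumption. The per-patient loss is exact: (14 − d)/14 of the window for discharge on day d before day 14.

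The effect on the comparison between arms is unknown. It is negligible if nearly all patients stay 14 days or more, and it could matter if many leave earlier and stay differs by arm. The illustrated ratios and event counts belong to their scenarios only.

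Severity is modest. This is a correction to how one named harm is counted, and the primary endpoint, sample size and efficacy interim do not depend on it.

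**What to change.** Reconcile Section 5.3E with the synopsis on one fixed window. Delete the closing parenthesis and the discharge limit from the SSI item in 5.3E, and count SSIs to day 14 after transplant in every patient, in or out of hospital. State that infections after discharge and up to day 14 are taken from the EMR follow-up in Section 4.1, by the same review in both arms. Section 8.2 provides blinded review only for the primary outcome, so have the SSI review done by staff unaware of arm where existing staff allow. Report the number discharged before day 14 by arm beside the 14-day SSI proportions.

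The cost is a protocol amendment, which under Section 17.1 needs prior ethics approval, and a short EMR check at each of the three sites. Infections treated elsewhere after discharge may still be missed, so some dependence on stay can remain. The discharge counts by arm would show how much room there is for it.

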5.4 Other Evaluations

- A. Fluid totals Fluid intake (crystalloid, colloid, and blood products) and output (estimated blood loss, urine output) will be tallied and recorded at defined time points in each case: start of surgery (skin incision), clamping of the hepatic artery, 15 minutes post-reperfusion of the of the portal vein, completion of the hepatic artery, completion of the bile duct, and end of surgery (skin closure).
- **B.** Time at target temperature range The percentage of time within the target core temperature range (34-35 °C for the Experimental Treatment, and 36.5-37.5 °C for the Control) as measured by bladder temperature, will be calculated.

6 SUBJECT SELECTION

6.1 Study Population

Subjects with a diagnosis of liver disease who meet the inclusion and exclusion criteria will be eligible for participation in this study.

6.2 Inclusion Criteria

- 1. Male or female \geq 18 years of age at the time of LTx.
- 2. Undergoing LTx from a donor after neurologic determination of death (DNDD).
- 3. Written informed consent obtained from subject or subject's legal representative and ability for subject to comply with the requirements of the study.

6.3 Exclusion Criteria

- 1. Undergoing LTx from a donor after cardiac death (DCD)
- 2. Undergoing LTx for acute liver failure (ALF)
- 3. Undergoing LTx from a living donor
- 4. Undergoing simultaneous liver-kidney transplantation
- Subject has a diagnosis of portopulmonary hypertension (defined as mean pulmonary artery pressure ≥ 25 mmHg, pulmonary vascular resistance > 3 Woods Units, and pulmonary artery wedge pressure < 15 mmHg in the setting of portal hypertension without another known cause).

- 6. Subject received RRT, including hemodialysis or continuous renal replacement therapy, within a week prior to liver transplantation.
- 7. Subject is intubated and/or mechanically ventilated prior to entering the operating room LTx.
- 8. Presence of a condition or abnormality that in the opinion of the Investigator would compromise the safety of the patient or the quality of the data.

7 CONCURRENT MEDICATIONS

Not applicable.

8 STUDY TREATMENTS

8.1 Method of Assigning Subjects to Treatment Groups

Up to 230 eligible patients will be randomly assigned to the Experimental Treatment (mild hypothermia) or Control (normothermia) groups in a 1:1 ratio using a block randomization scheme with a randomly chosen block size of 6 or 8 for each block. The randomization scheme was developed by Randomize.net and is accessed through a secure web portal.

8.2 Blinding

Due to the objectives of the study, the identity of test and control treatments will not be known to patients. The following study procedures will be in place to ensure single-blind administration of study treatments.

Access to the randomization code will be strictly controlled. The randomization code will not be revealed until the patient has entered the operating room for liver transplantation. The study protocol will be completed in its entirety while the patient is in the operating room under general anesthesia. Therefore, it will be impossible for the patient to know the treatment assignment until the protocol is complete.

No attempt will be made to blind the study doctors (anesthesiologists), who are investigators in the study, to the treatment assignment, as they will be the ones administering and monitoring the temperature protocol during LTx.

Research staff assigned to adjudicate the Primary Outcome (presence or absence of AKI within 72 h of LTx) will be blinded to the treatment assignment and the intraoperative anesthesia record showing the patient's core temperature. Only the preoperative and postoperative values of sCr will be necessary to adjudicate the Primary Outcome.

The study blind will be broken on completion of the clinical study and after the study database has been locked.

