3 STUDY OBJECTIVES

3.1 Primary Objective

The primary objective is to assess whether or not mild hypothermia has a protective effect on early AKI after liver transplantation. We hypothesize that mild hypothermia will protect against intraoperative AKI during LTx. We will measure the proportion of patients that develop AKI in the early post-transplant period (≤ 72 hours) as our primary efficacy outcome. This time window is likely to reflect AKI occurring due to intraoperative events,^{22,32} and therefore has potential to be modulated by the study intervention. Serum creatinine measurements will be recorded by observers blinded to the treatment arm, and the presence and severity of AKI adjudicated according to the latest criteria.^{33,34}

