5 CRITERIA FOR EVALUATION

5.1 Primary Efficacy Endpoint

The primary efficacy endpoint is the incidence of AKI within 72 hours after LTx. The International Club for Ascites (ICA) 2015 criteria, a revision of the KDIGO criteria for patients with cirrhosis, will be used to define AKI.³³ The definitions are as follows:

- AKI: increase in sCr \ge 0.3 mg/dL within a 48 hour time window, or a percentage increase \ge 50% from baseline, or initiation of RRT.
- **Baseline sCr**: the most recent value of sCr prior to LTx

A predefined subgroup analysis of the primary outcome will be performed in patients undergoing liver transplantation for hepatocellular carcinoma (HCC) with Model for Endstage Liver Disease exception points.

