5.2 Secondary Efficacy Endpoints

- A. The distribution of the stages of AKI within 72 hours after liver transplantation. The ICA 2015 criteria will be used to define the stages of AKI as follows:
 - AKI Stage 1: increase in sCr ≥ 0.3 mg/dL, or an increase in sCr ≥ 1.5-fold and ≤ 2-fold from baseline.
 - **AKI Stage 2**: increase in sCr > 2-fold and \leq 3-fold from baseline.
 - AKI Stage 3: increase in sCr > 3-fold from baseline, or sCr \ge 4.0 with an acute increase of \ge 0.3 mg/dL, or initiation of RRT
- **B.** Duration of intensive care unit (ICU) stay.

- AKI may worsen volume overload, electrolyte abnormalities, and metabolic acidosis, all of which can lead to prolongation of ICU stay.
- **C.** Duration of hospital stay.
- **D.** One-year survival rate.
 - AKI after LTx is a negative predictor of mortality.^{17,20}
- **E.** Incidence of post-operative renal replacement therapy within 7-days, at 30-days, and at 1 year after transplant.
 - LTx is a predictor of developing chronic renal failure.³⁷
- F. Persistent renal dysfunction at 90-days and 1-year after transplant.
 - Presence of a reduction in GFR by ≥ 25 mL/min or ≥ 50% from baseline (Kellum et al.)
 - We are aware that patients may not have lab values available from dates exactly 30-days, 90-days, and 1-year after the date of transplantation surgery. In order to standardize our data collection, we have developed rules to determine the appropriate serum creatinine values to record. The rules are as follows:

1 year follow up: preferences (in order of preference) for selecting serum creatinine value to record:

- 1. Serum creatinine value within 1 month after 1-year follow-up date.
- 2. Serum creatinine value within 1 month before 1-year follow-up date.
- 3. Serum creatinine value collected at a date after 1-year follow-up date that is beyond 1 month but closest to the follow-up date.

30 and 90 day follow up:

- The serum creatinine value recorded must have been collected on or post the 30 and 90 follow-up dates. Select the serum creatinine value on or closest to the 30- and 90-day follow-up dates.
- **G.** Change in serum NGAL levels from baseline (start of surgery) to 2 hours after reperfusion of the liver graft (opening of the portal vein).
 - NGAL has been shown to be an early marker of AKI in LTx,²⁴ and as such has the potential to be modulated by the study intervention

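### Section 8.2 says creatinine alone is enough to adjudicate AKI, but 5.1 and 5.2A also count the start of renal replacement therapy (RRT) on its own

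*Combined protocol and SAP*

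**What the plan says.** Section 5.1 sets the window: "The primary efficacy endpoint is the incidence of AKI within 72 hours after LTx". It then defines AKI by three alternatives: a rise in serum creatinine (sCr) of at least 0.3 mg/dL within 48 hours, or a rise of at least "50% from baseline, or initiation of RRT". Section 5.2A, on the distribution of AKI stages, uses the same device. Stage 3 is met by a more than three-fold rise, or by sCr of at least 4.0 with an acute increase of at least "0.3 mg/dL, or initiation of RRT".

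Two places describe the data used to apply these definitions. Section 3.1 says: "Serum creatinine measurements will be recorded by observers blinded to the treatment arm", and adds that presence and severity of AKI are adjudicated by current criteria. Section 8.2 says that the adjudicating staff "will be blinded to the treatment assignment and the intraoperative anesthesia record showing the patient's core temperature", and continues: "Only the preoperative and postoperative values of sCr will be necessary to adjudicate the Primary Outcome".

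RRT is collected as secondary endpoint E in section 5.2, as post-operative incidence within 7 days, at 30 days and at 1 year. Nothing in the documents links that item to the 72-hour adjudication.

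**The concern.** If starting RRT counts as AKI whatever the creatinine, creatinine values cannot be sufficient to decide the primary outcome. The statement in 8.2 and the definition in 5.1 do not agree, and 8.2 is the only place that says what adjudicators need. Staff could build a creatinine-only adjudication form, follow 8.2 exactly, and not apply the endpoint as defined.

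Two kinds of error would follow. A patient who starts RRT without reaching either creatinine threshold would be recorded as having no AKI, which is an error in the primary endpoint. A patient who starts RRT after a creatinine rise in the Stage 1 or Stage 2 range would be given that stage and not Stage 3. The second error leaves the primary outcome intact but affects the first-listed secondary endpoint, which section 15.4 tests by chi-square and a proportional odds model.

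**Working it through.** **1. The texts side by side.**

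| Section | Role | Creatinine | RRT start |
|---|---|---|---|
| 5.1 | Defines AKI (primary) | yes | yes, stand-alone |
| 5.2A | Defines Stage 3 | yes | yes, stand-alone |
| 3.1 | Data recorded by blinded observers | yes | not mentioned |
| 8.2 | Data needed to adjudicate the primary outcome | yes, described as all that is needed | not mentioned |
| 5.2E | Separate secondary endpoint | – | collected, not linked to 72 hours |

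The definitions use two kinds of information and the adjudication text supplies one. This settles the inconsistency without arithmetic. It also does not depend on what RRT does to later creatinine values, which the documents do not discuss.

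**2. The plan's own sample size.** Inputs from section 15.6: control AKI 68%, a 30% reduction, 80% power, two-sided alpha 0.05. Section 15.5.1 gives a final alpha of 0.0492. Read as relative, the reduction gives 0.68 × 0.70 = 0.476, a difference of 20.4 points.

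- Uncorrected two-proportion formula: n = [z(1−α/2)·√(2p̄q̄) + z(0.80)·√(p₁q₁ + p₂q₂)]² / (p₁ − p₂)². With p̄ = 0.578 this gives 91 per arm at alpha 0.05 and 92 at 0.0492.
- With the continuity correction: 101 per arm at either alpha.

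The stated 101 per arm is reproduced and is not in dispute.

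**3. Cost of missed RRT-only cases.** No 72-hour RRT rate is given, so this step is an assumption shown as a range. Let m be the share of control patients whose AKI is met only through RRT and is missed, and let the share in the hypothermia arm be 0.7m, in line with the planned 30% reduction. The observed rates become 0.68 − m and 0.476 − 0.7m. Power is for the uncorrected test:

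power = Φ{[(p₁ − p₂)√n − z(1−α/2)·√(2p̄q̄)] / √(p₁q₁ + p₂q₂)}, with n = 101 and α = 0.0492.

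| m | Controls missed (101 × m) | Observed rates | Difference | Power |
|---|---|---|---|---|
| 0 | 0 | 68.0% v 47.6% | 20.4 | 83.9% |
| 1% | 1.0 | 67.0% v 46.9% | 20.1 | 82.6% |
| 2% | 2.0 | 66.0% v 46.2% | 19.8 | 81.2% |
| 3% | 3.0 | 65.0% v 45.5% | 19.5 | 79.8% |

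The first row exceeds 80% because 101 came from the continuity-corrected formula and the power shown is uncorrected. If every missed case were a control, power would be 79.9%, 75.3% and 70.3% at m = 1%, 2% and 3%.

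**4. Direction.** Start from 68% v 47.6% and vary only where the missed cases fall:

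- 2% of controls, 1.4% of hypothermia patients: 66.0 − 46.2 = 19.8 points, narrower.
- 2% of each arm: 66.0 − 45.6 = 20.4 points, unchanged.
- 2% of controls, 4% of hypothermia patients: 66.0 − 43.6 = 22.4 points, wider.

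**5. Staging.** Section 2 puts Stage 3 at 12% at the lead centre, or 0.12 × 101 ≈ 12 controls. That figure includes three-fold creatinine rises, which creatinine already detects, and it is not tied to 72 hours. It shows only that the Stage 3 cell is small, so a few misgraded patients would be a visible part of it. It does not measure how many would be misgraded.

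**The case against.** The best defence is that 8.2 says creatinine is all that is needed, not all that is allowed. The sentence follows the blinding rule and reads as a reason why hiding the anesthesia record does no harm. Adjudicators are kept from the treatment assignment and that record only, so postoperative RRT information is not withheld. Section 3.1 points to the criteria, 5.1 states them in full, endpoint E covers a period that contains the 72 hours, and section 4.1 provides for analysis of electronic record data after surgery. An adjudicator who applies 5.1 literally has to count RRT. Moreover, the creatinine thresholds are low, so many RRT patients may qualify through creatinine anyway.

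Most of this stands, and it limits the point. The gap is unreconciled wording; it is neither a wrong endpoint nor uncollectable data. It does not remove the point, because the one sentence on what adjudication requires is incorrect under 5.1 and nothing directs RRT start times to the adjudicators.

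A reader might go further in four ways that the documents do not support:

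- *Adjudicators are barred from RRT data.* No passage says so.
- *The error must bias towards no difference.* Step 4 shows it can narrow, preserve or widen the difference.
- *RRT begun during surgery is hidden because the anesthesia record is withheld.* The documents never mention intraoperative RRT or say where it would be recorded, and endpoint E concerns post-operative RRT.
- *Every RRT patient's primary outcome depends on RRT information.* Only a patient who meets neither creatinine criterion is lost from the primary endpoint.

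**Conclusion.** The inconsistency is real: 8.2 and 3.1 describe a creatinine-only adjudication of an endpoint that 5.1 and 5.2A define by creatinine or RRT. Followed as written, 8.2 would miss RRT-only AKI, and the creatinine data named in 3.1 would under-stage RRT patients with smaller rises.

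The size is unknown. For the binary endpoint it is probably small: power falls from 83.9% to 82.6–79.8% if 1% to 3% of controls are missed and the hypothermia arm has 0.7 times that share. Both the range and the ratio are assumptions. A larger imbalance towards controls would cost more, and an imbalance the other way would exaggerate the effect. The stage distribution is more exposed, though 8.2 itself speaks only of the primary outcome. The planned 101 per arm is unaffected.

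**What to change.** Amend 8.2 and 3.1 to say that blinded adjudicators receive pre- and postoperative sCr together with the masked date and time of any RRT initiation within the 72-hour window, and apply 5.1 and 5.2A as written. Record the same rule in the SAP that section 15 says is still to be written.

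No separate rule is needed for creatinine drawn after RRT starts, because such a patient already counts as AKI and Stage 3.

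The cost is a sentence in each of two sections and one field on the adjudication form. The information is obtainable from the data for endpoint E, provided that the start date and time are captured and not only a yes or no within 7 days. An RRT start time shows neither the assigned arm nor the core temperature, so the blind is kept. The sample size and the analysis methods stay as they are.
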